9.5 Study Size

An enrollment total of 75 in the exposed group and 150 in each of the 2 comparison groups after 10 years is anticipated. Given that these numbers assume the prevalence of exposure is sufficient to support recruitment of these numbers, the feasibility of achievement will be re-evaluated at each annual interim review of the data.

Based on previous experience with MotherToBaby/OTIS Pregnancy Studies, we estimate that subjects will be an average of 7-10 weeks post-LMP at the time of enrollment. Given this mean gestational timing at enrollment, the anticipated spontaneous abortion/stillbirth rate is 10%, the estimated elective abortion rate is 5%, and the estimated lost to follow-up rate is 5%. This results in an estimated 71 observable pregnancies of which 60 are estimated to result in live births in cohort 1 (exposed group), and an estimated 142 observable pregnancies of which 120 are estimated to result in live births in cohorts 2 and 3 (control groups).

Baseline rates of major structural **birth** defects, spontaneous abortion, premature delivery, and small for gestational age, as well as the standard deviation for mean birth weight of full-term infants were based on previous MotherToBaby/OTIS studies and on general population data (Table 3). With the sample size estimated above, at $\geq 80\%$ power, alpha of 0.05, two-tailed tests of significance (except as noted below for pattern of minor structural **birth** defects), and each comparison group independently compared to the exposed group, the minimum effect sizes detailed in Table 3 will be detectable.

With respect to the evaluation of minor malformations, the strength of this study design is in the ability to examine the data for a pattern of minor and/or major structural **birth** defects, given that the known human teratogens are typically associated with a pattern as opposed to isolated major **structural** birth defects. A baseline prevalence estimate of 1% has been used for a specific pattern of minor **structural birth** defects. The RR detectable with this sample size is 10.0. This represents a 10% birth prevalence of a specific pattern (ie, approximately 6 children in the exposed sample), which is comparable to the birth prevalence of a specific pattern in other known human teratogens of moderate risk such as the anticonvulsant medications.

For the primary outcome, the study is powered to detect that the Evolocumab-Exposed group has a 3.8-fold (or greater) risk of all major **structural** birth defects combined relative to the risk in the primary comparison group. This level of risk for teratogenicity is below that observed for other, but not all, agents deemed teratogenic. Importantly, known human teratogens tend to be associated with increased risks for specific patterns of birth defects and are not associated with increased risks for any and all major **structural birth** defects. For this reason, the analysis of the primary outcome, combined with evidence of a cluster or pattern of defects, provides the best ability for evaluation of teratogenic risk.

Table 3. Sample Size and Power for a Specified Effect Size Based on Minimal Sample Size^a

Outcome	N in Cohort 1	N in Cohort 2 or 3	Baseline Rate	RR	Power ^b
Major structural birth defects ^c	71	142	4% ^d	3.8	84%
Specific pattern of 3 or more minor structural birth defects	60	120	1% ^e	10.0	71% ^f
Spontaneous abortion/stillbirth	71	142	10% ^g	2.5	88%
Preterm delivery	60	120	9% ^h	2.8	85%
SGA	60	120	10% ⁱ	2.6	80%
Small for age (postnatal growth deficiency)	46	108	10%	2.8	82%
Neurodevelopmental outcomes (Phase II)	40	40	--	0.5 SD ^j	80%
Inadequate immune response (via IgG tetanus antibody status)	60	120 ^k	20% ^l	2	82%

Definitions: Ig = immunoglobulin; RR = relative risk; SGA = small for gestational age.

^a Software used to calculate power and effect size: OpenEpi v3 (Dean et al, 2015).

^b Based on Fisher's Exact Test or chi-square, two-tailed, alpha 0.05, except for specific pattern of 3 or more minor anomalies as noted below.

^c Primary endpoint.

^d Baseline rate in comparison group based on 4.1% in statin exposed (Winterfeld et al, 2013).

^e Baseline rate in comparison group expected to be 0-1% based on no evidence of a pattern.

^f Based on one-tailed Fisher's Exact Test, alpha 0.05.

^g Baseline rate based on 13.6% in statin exposed (Winterfeld et al, 2013) and 4.4% (Chambers et al, 2013) (rate influenced by gestational time of enrollment).

^h Baseline rate based on 16.1% (Winterfeld et al, 2013) and 6.2% (Toleikyte et al, 2011).

ⁱ Baseline rate based on 5.0% for low birth weight defined as < 5th centile which translates to 10% for SGA defined as < 10th centile (Toleikyte et al, 2011).

^j Minimum detectable difference calculated for neurodevelopmental outcomes as a continuous variable (instead of RR for categorical variables).

^k Estimating 60 infants per cohort.

^l Baseline rate based on Marshall et al (2010).

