9.3.2.2 Secondary Outcomes

9.3.2.2.1 Pregnancy Outcomes

- Rate of spontaneous abortion where spontaneous abortion is defined as non-deliberate fetal death which occurs prior to 19 completed weeks post-LMP
- Rate of elective abortion where elective abortion is defined as deliberate termination of pregnancy at any time in gestation
- Rate of stillbirth where stillbirth is defined as non-deliberate fetal death anytime in gestation at or after 19 completed weeks post-LMP
- Rate of premature delivery where premature delivery is defined as live birth prior to 37.0 weeks gestation as counted from LMP (or ultrasound adjusted date)

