9.7.2.4.1 Description of Study Enrollment

Outcome	Analysis Subset
Major Structural Birth Defect Among Live Births	All pregnancies ending in at least 1 live born infant
Major Structural Birth Defects Among All Pregnancies Excluding Lost to Follow-Up	All pregnancies excluding lost to follow-up
Spontaneous Abortion	Pregnancies enrolled prior to 20 weeks' gestation
Stillbirth	Pregnancies enrolled excluding lost to follow-up
Preterm Delivery	Pregnancies enrolled prior to 37 completed weeks' gestation, excluding pregnancies ending in twin or higher order multiple births
Minor Structural Birth Defects	Live born infants who have received the dysmorphology examination
Small for Gestational Age Infants	Live born infants excluding twin or higher order multiple births
Breastfeeding	Pregnancies ending in at least 1 live born infant
Postnatal Growth	Live born infants followed up to 1 year postpartum, excluding twin or higher order multiple births
Serious or Opportunistic Infections	Live born infants followed up to 1 year postpartum
Immune Function	Live born infants who received the tetanus titer testing
Response to vaccines	Live born infants who received at least one vaccine
Neurodevelopment	Live born infants for whom developmental screening questionnaires were completed or face-to-face testing was completed

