9.7.2.5.2 Secondary Analysis

The following will comprise the secondary analyses:

1. Comparison of all secondary outcomes between the Specific Evolocumab-Exposed cohort and Comparison Group I
2. Comparison of the primary and all secondary outcomes between the Specific Evolocumab-Exposed cohort and Comparison Group II

The comparison of the prevalence of the total proportion of major structural **birth** defects between the Specific Evolocumab-Exposed cohort and Comparison Group II will be among all live births and, separately, among all pregnancies excluding those lost to follow-up. The comparison of the prevalence of ≥ 3 minor malformations between the Specific Evolocumab-Exposed cohort and each of the 2 comparison groups will be among children who receive the dysmorphological examination. The comparison of IgG-tetanus antibody status (test negative or indeterminate vs test positive) by group (Exposed, Comparison Group I, Comparison Group II) among those in the biological sample sub-study.

In each cohort we will separately calculate the proportion of all pregnancies ending in live birth, spontaneous abortion, stillbirth, elective termination, and lost to follow-up; crude comparisons will be made between cohorts.

The evaluation for a pattern of minor structural **birth** defects will be conducted using the following steps:

1. A comparison among groups of the proportion of infants with any 3 or more minor structural **birth** defects will be made without regard to pattern
2. Among infants with 3 or more minor **structural birth** defects, the Evolocumab-Exposed group will be examined for evidence of a specific pattern of 3 or more defects in any 2 or more children. If such a pattern is identified, Comparison Groups I and II will be evaluated for any evidence of the same pattern.

In each cohort among all live born infants we will separately calculate the proportion of premature delivery, small for gestational age on weight, length or head circumference, and rates of serious infections, hospitalizations, adverse vaccine reactions, and adverse neurodevelopmental outcomes; crude comparisons will be made between cohorts.

Mean birth weight, length and head circumference for full-term live born infants will be compared between cohorts. Postnatal growth parameters will be compared using the proportion of infants ≤ 10 th centile for sex and age with respect to weight, height, or head circumference.

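### Table 3's pregnancy-loss row prints 88% power where its inputs give about 78–81%, and it sizes a combined outcome that the protocol defines and compares only as two separate outcomes

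*Protocol*

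**What the plan says.** **Sizing.** Section 9.5 of the protocol assumes that "the anticipated spontaneous abortion/stillbirth rate is 10%, the estimated elective abortion rate is 5%, and the estimated lost to follow-up rate is 5"%. It states that the effects in Table 3 are detectable with at least 80% power at "alpha of 0.05, two-tailed tests of significance", each comparison group being tested separately against the exposed group. The Table 3 row is labelled "Spontaneous abortion/stillbirth" and gives 71 and 142 pregnancies, a 10% baseline, RR 2.5 and 88% power. Footnote b describes the power column: "Based on Fisher's Exact Test or chi-square, two-tailed, alpha 0.05". The one exception it makes is the row on patterns of minor defects.

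**Source of the 10%.** Footnote g cites two published rates, 13.6% and 4.4%, and notes that the rate depends on when women enrol. It gives no division between the two outcomes. The paragraph of section 9.5 that introduces Table 3 lists the baseline as that of spontaneous abortion, without mentioning stillbirth.

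**Outcomes and analysis.** Section 9.3.2.2.1 lists spontaneous abortion (non-deliberate loss before 19 completed weeks) and, as a separate item, "Rate of stillbirth where stillbirth is defined as non-deliberate fetal death anytime in gestation at or after 19 completed weeks post-LMP". Section 9.7.2.4.1 gives each its own subset: for spontaneous abortion, "Pregnancies enrolled prior to 20 weeks' gestation"; for stillbirth, enrolled pregnancies other than those lost to follow-up. Section 9.7.2.5.2 says that in each cohort "we will separately calculate the proportion of all pregnancies ending in live birth, spontaneous abortion, stillbirth, elective termination, and lost to follow-up", with crude comparisons between cohorts. No section of the protocol defines or compares the two combined.

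**The concern.** A reader uses Table 3 to judge what a null result on pregnancy loss would rule out. This row misleads in two independent ways: the power does not follow from the inputs, and the inputs describe an outcome that the protocol does not list. Both errors run in the favourable direction. Section 9.7.2.1 describes the cohort analysis as hypothesis testing at alpha 0.05, and section 11.2 treats spontaneous abortion and stillbirth in exposed pregnancies as serious adverse events, so the sensitivity claimed here should be right. The row does not set the sample size, and these are secondary outcomes. What is at stake is the accuracy of a stated power.

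**Working it through.** **Inputs.** All come from section 9.5 and Table 3: n1 = 71 (75 × 0.95 = 71.25), n2 = 142 (150 × 0.95 = 142.5), p0 = 0.10, RR = 2.5, so p1 = 0.25; two-tailed alpha 0.05.

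**Step 1: reproduce the 88%.** Normal approximation with pooled variance under the null:

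power = Φ{ [ (p1 − p0) − 1.96·√( p̄(1 − p̄)(1/n1 + 1/n2) ) ] / √( p1(1 − p1)/n1 + p0(1 − p0)/n2 ) }

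- p̄ = (71 × 0.25 + 142 × 0.10)/213 = 0.15
- null standard error = √(0.1275 × (1/71 + 1/142)) = 0.0519
- alternative standard error = √(0.1875/71 + 0.09/142) = 0.0572
- (0.15 − 1.96 × 0.0519)/0.0572 = 0.844, so power = 80.1%

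Exact enumeration of the two binomial distributions gives 77.6% for two-tailed Fisher and 80.8% for Pearson chi-square. Other two-sided variants do not reach 88%: continuity-corrected 74.5%, unpooled 74.6%, arcsine 79.3%, no loss to follow-up (75 and 150) 82.0%. A one-sided test gives 87.1%, but footnote b rules that out for this row. Nor does it explain the table: one-sided power would be 87.4% for preterm delivery (printed 85%) and 85.4% for small for gestational age (printed 80%). With the pooled formula, 88% needs an RR of about 2.73.

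**Step 2: what the 10% covers.** Section 9.5 expects 60 and 120 live births. From those enrolled, 75 × (1 − 0.10 − 0.05 − 0.05) = 60 and 150 × 0.80 = 120. The 10% therefore carries all non-deliberate loss, as the sentence in section 9.5 says. If it were spontaneous abortion alone, the live-birth count would leave no room for stillbirth.

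**Step 3: power for the outcomes as listed.** The split is not in the documents, so the baselines below are assumptions. RR 2.5, 71 against 142, two-tailed 0.05, exact enumeration:

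| Outcome | Assumed baseline | Fisher | Chi-square |
|---|---|---|---|
| Combined, or spontaneous abortion if it is the whole 10% | 10% | 77.6% | 80.8% |
| Spontaneous abortion | 9.5% | 75.0% | 78.5% |
| Spontaneous abortion | 9% | 72.3% | 75.9% |
| Spontaneous abortion | 8% | 66.3% | 70.2% |
| Stillbirth | 3% | 28.5% | 31.9% |
| Stillbirth | 2% | 21.2% | 24.1% |
| Stillbirth | 1% | 10.6% | 17.2% |

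The RR with 80% power (pooled formula) is 2.5 at a 10% baseline, about 2.6 at 9% and about 2.8 at 8%.

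**Step 4: separate the two faults.** By Fisher, moving from 88% to 77.6% is a loss of 10.4 points from the printed figure alone. Splitting then costs 2.6 points at 9.5%, 5.3 at 9% and 11.3 at 8%. At 9–9.5%, most of the gap from 88% for spontaneous abortion therefore comes from the figure that does not reproduce.

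**The case against.** Several points on the other side stand.

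- **A reader might infer that at least 80% power holds for neither outcome.** The documents do not establish that. Section 9.5 in one place names the baseline as spontaneous abortion alone. On that reading the chi-square power is 80.8%, which meets the claim, though Fisher at 77.6% does not. Any lower figure depends on an assumed split.
- **A reader might apply the 4.4% in footnote g to spontaneous abortion and conclude that power is about 40–44%.** That uses one end of the range. The other cited rate, 13.6%, gives 91–93%. The documents do not say whether either rate covers spontaneous abortion alone.
- **Low power for stillbirth contradicts nothing printed.** Table 3 has no row for stillbirth alone, and it omits other secondary outcomes such as elective abortion and breastfeeding. A missing row is not an error.
- **The smaller subset for spontaneous abortion probably matters little.** Enrolment is expected at 7–10 weeks on average, so few women should join after 20 weeks. The restriction can only leave the numbers at 71 and 142 or reduce them, but the reduction cannot be quantified. Section 9.7.2.5.2 also expresses both proportions over all pregnancies.
- **Section 9.9 already warns that power is limited for primary and secondary endpoints,** and section 9.2.2 continues recruitment for 10 years whatever the count.
- **A separate analysis plan may define a combined outcome.** None was available here, so the point is limited to what the protocol defines.

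None of this rescues the 88%, or reconciles the row's label with the listed outcomes.

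**Conclusion.** Two corrections are due in one row. The 88% is wrong under the stated two-tailed tests: the inputs give about 78–81%. That result needs no assumption beyond the table's own entries. The row also describes combined loss, while the protocol lists, subsets and compares spontaneous abortion and stillbirth separately, and section 9.5 is inconsistent about which of these the baseline describes. The size of the second effect depends on an unstated split: a few points for spontaneous abortion if stillbirth is rare, about 11 points if it takes 2 of the 10 percentage points. No split brings either outcome up to 88%, because neither component can exceed the 10% total and even the whole 10% gives only 78–81%. This should be corrected, but it concerns a secondary outcome and does not affect the sample size or the primary analysis.

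**What to change.** 1. In Table 3, replace 88% with about 78–81% for the present inputs and name the test used.
2. Make the row match the planned analysis. State it for spontaneous abortion, with a baseline for that outcome alone, the expected number enrolled before 20 weeks, and the recomputed power or the RR detectable with 80% power. Align the two descriptions of the baseline in section 9.5.
3. Add a note that stillbirth alone is not powered at RR 2.5.
4. If the sponsor prefers to keep a combined row, define combined non-deliberate fetal loss in sections 9.3.2.2.1, 9.7.2.4.1 and 9.7.2.5.2 as an additional comparison. The two listed outcomes should keep their present status.

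The cost is a few lines of text, one recomputed row and a less favourable stated power. Both events are already collected, so no new data are needed.

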a variety of factors which may be related to exposure and to pregnancy outcome, such as maternal cholesterol levels and comorbidities including cardiovascular disease history, obesity, diabetes, and hypertension. The use of a disease-matched comparison group addresses to some extent the issue of confounding by indication.

Misclassification bias due to poor recall is thought to be reduced in prospective study designs such as this. In addition, each subject is interviewed at several predetermined intervals during pregnancy. Misclassification bias regarding outcome is minimized in this study design through the use of a specialized physical examination and a standardized evaluation protocol.

Another strength of the study design is the anticipated minimal lost to follow-up rate. Based on previous experience of the investigators in the MotherToBaby/OTIS Pregnancy Studies, and the frequent subject contact, lost to follow-up is typically < 5% and therefore is not expected to pose a threat to the validity of study results. A subject meeting the criteria for enrollment is considered “lost to follow-up” if follow-up information on the outcome (live birth, fetal loss) is not obtainable, or for a live birth if the birth defect status is designated as “unknown” as of 12 months following the estimated due date. Before a **subject** is designated as lost to follow-up, the subject or reporter receives at least 3 reminder telephone calls (documented in database) followed by written correspondence; alternative contact information that is requested upon enrollment is also utilized. All follow-up attempts are documented. Losses to follow-up are tallied in the Registry Interim Reports. No imputation of missing data is planned.

Finally, the primary strength of the cohort study portion of the Registry is its sensitivity for detection of a pattern of malformation. As the known teratogens are associated with specific patterns of malformation, this study design, by virtue of providing study-related dysmorphological evaluation of prospectively ascertained and exposed infants, has the unique capability of detecting within reasonable limits such a pattern if it exists.

10. Protection of Human Subjects

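### Table 3 plans postnatal growth on 46 exposed v 108 comparison infants, an unexplained departure from the protocol's own 60 v 120, and the named tests do not give the stated 82% power

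*Protocol*

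**What the plan says.** Protocol Section 9.5 takes off losses at the same rates in every group. It states that "the estimated lost to follow-up rate is 5" percent, and it sets spontaneous abortion or stillbirth at 10% and elective abortion at 5%. For the exposed cohort the result is 71 observable pregnancies, "of which 60 are estimated to result in live births in cohort 1 (exposed group"). For each comparison cohort it is 142, "of which 120 are estimated to result in live births in cohorts 2 and 3 (control groups").

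Table 3 then uses 60 and 120 for the minor-defect pattern, preterm delivery and small for gestational age. The growth row, headed "Small for age (postnatal growth deficiency"), gives 46 exposed, 108 comparison, baseline 10%, RR 2.8, power 82%. It has no footnote on its sample sizes. Footnote b gives the tests as Fisher's exact or chi-square, two-sided at 0.05, and the text of Section 9.5 claims at least 80% power for everything except the minor-defect pattern.

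Section 9.7.2.4.1 restricts the growth analysis to singletons followed to 1 year. Section 9.9 says that "lost to follow-up is typically < 5% and therefore is not expected to pose a threat to the validity of study results" and that "No imputation of missing data is planned".

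**The concern.** The growth row cannot be obtained from the live-birth numbers by any rule that the protocol states, and it assumes that exposed infants go unmeasured at more than twice the comparison rate. Two readings are open.

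- **A slip.** The exposed sample size, and perhaps the power, is then misreported for a secondary safety outcome.
- **Intended.** The sponsor then plans on growth data that are missing unequally by exposure, while the protocol's only assurance about loss concerns something else and no imputation is planned. Missingness that differs by exposure can push a complete-case relative risk either way, including towards hiding a growth deficit.

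**Working it through.** **Inputs.** Section 9.5: 75 and 150 enrolled; 5% lost; 10% + 5% pregnancy losses. Table 3, growth row: 46, 108, 10%, RR 2.8, 82%. Footnote b: Fisher's exact or chi-square, two-sided 0.05.

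**Step 1. The protocol's live births.**
- Exposed: 75 × 0.95 = 71.25; 71.25 × 0.85 = 60.6, stated as 60.
- Comparison: 150 × 0.95 = 142.5; 142.5 × 0.85 = 121.1, stated as 120.

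The 5% loss is thus already inside 60 and 120.

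**Step 2. The further shortfall.**
- Exposed: (60 − 46)/60 = 14/60 = 23.3%.
- Comparison: (120 − 108)/120 = 12/120 = 10.0%.
- Ratio: 108/46 = 2.35, not 2.
- A 10% loss in both groups would leave 0.90 × 60 = 54 and 0.90 × 120 = 108. A further 5% loss in both would leave 57 and 114.

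**Step 3. Do the other rows or the analysis subset explain it?**
- Neurodevelopment is 40 v 40, but Section 9.4.5.2 sets that target.
- Immune response is 60 v 120, with footnote k stating 60 infants per cohort, in line with the target in Section 9.4.7.
- All other rows are 71 v 142 or 60 v 120.
- Multiple births are also excluded for small for gestational age and preterm delivery, which stay at 60 v 120. The 1-year condition applies to every group.

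So nothing stated produces an imbalance for growth alone.

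**Step 4. Reproducing the 82%.** The exposed rate is 0.10 × 2.8 = 0.28. With a pooled variance under both hypotheses:
- pooled p = (46 × 0.28 + 108 × 0.10)/154 = 0.1538
- SE = √[0.1538 × 0.8462 × (1/46 + 1/108)] = 0.0635
- power = Φ(0.18/0.0635 − 1.96) = Φ(0.874) = 80.9%

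This is within two points of the stated 82%.

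**Step 5. Power with the tests in footnote b.** This sums the binomial probabilities of every pair of counts that the test rejects, at 28% v 10%.

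| N exposed v comparison | Chi-square | Fisher | Pooled normal |
|---|---|---|---|
| 46 v 108 (as stated) | 79.1% | 73.6% | 80.9% |
| 54 v 108 (10% loss in both) | 83.2% | 78.8% | 83.8% |
| 46 v 92 (23.3% loss in both) | 76.5% | 71.4% | 77.6% |

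At 46 v 108 neither named test reaches 80%. The stated 82% lies within two points of 46 v 108 by the pooled approximation, and of 54 v 108 by chi-square or the pooled approximation. It therefore does not identify the intended sample size.

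**Step 6. What unequal missingness could do (illustration).** Assume a true deficiency rate of 10% in both groups (RR 1.0) and the same risk r among unmeasured infants in each group. Then:
- exposed rate = (60 × 0.10 − 14r)/46
- comparison rate = (120 × 0.10 − 12r)/108

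| r | Exposed | Comparison | Complete-case RR |
|---|---|---|---|
| 0% | 13.0% | 11.1% | 1.17 |
| 5% | 11.5% | 10.6% | 1.09 |
| 10% | 10.0% | 10.0% | 1.00 |
| 20% | 7.0% | 8.9% | 0.78 |
| 30% | 3.9% | 7.8% | 0.50 |

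**The case against.** A reader might infer that 23% v 10% contradicts the under-5% loss in Section 9.9. It does not. That section defines loss as an unobtainable pregnancy outcome, or unknown birth-defect status 12 months after the due date, and Section 9.5 deducts it before reaching 60 and 120. Growth has a narrower subset and relies partly on later pediatric forms and new record releases (Section 9.4.4), so a larger shortfall can coexist with under 5% loss. What stands is that the assurance does not extend to growth.

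A reader might also infer that the plan fixes a crude comparison for growth. The sentence on crude infant comparisons in Section 9.7.2.5.2 does not list postnatal growth, and that section also plans adjusted comparisons. Adjusting for confounders would not by itself deal with missing measurements, however.

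The power gap is not special to this row. By the same exact chi-square calculation, major defects give 79.7% against a stated 84%, and spontaneous abortion or stillbirth 80.8% against 88%. The gap reflects the formula used and is no proof that 46 is wrong. That objection stands; it does not explain the sample sizes.

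Finally, these are planning numbers for a secondary outcome, not observed attrition, and missing-data detail may sit in a statistical analysis plan that is not at hand. That limits the point to what the protocol itself fixes: the row, its power and the scope of its assurance.

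**Conclusion.** The point holds as an unexplained and inconsistent planning row. The shortfall from live births is 23.3% v 10.0%, and no stated rule yields it. With the tests the protocol names, power is 79.1% or 73.6%, below both the stated 82% and the claimed 80%. These figures rest on the protocol's own 10% baseline and RR of 2.8.

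The documents do not show whether 46 is a slip or intended, so neither that 54 is the right number nor that differential loss will occur is established. Nor is bias established: the relative risks from 1.17 to 0.50 depend on an assumed risk among unmeasured infants, for which the protocol gives no figure, and there is no bias if that risk is 10%. For a secondary safety outcome, this warrants a correction but does not call the study into question.

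**What to change.** 1. Correct or justify 46 v 108 in Table 3. If a 10% loss in both groups was meant, the row becomes 54 v 108.
2. Restate the row's power and name the test or formula: 83.2% (chi-square) or 78.8% (Fisher) at 54 v 108, and 79.1% or 73.6% if 46 v 108 stays.
3. If the unequal shortfall is intended, give the reason in a footnote and state in Section 9.9 that the under-5% figure concerns pregnancy outcome or birth-defect status and does not cover growth. Add an analysis of postnatal growth weighted by the inverse probability of having a measurement, using data already collected such as birth size, gestational age and maternal covariates.

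The first two changes cost one table row. The third costs a sentence or two and one analysis on existing data, with slightly wider intervals. The weighting corrects only for missingness that the collected covariates explain.

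### Table 3's only minor-defect power figure (71% for a specific pattern at RR 10.0) does not follow from its own inputs and does not match the analysis written in section 9.7.2.5.2

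*Protocol*

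**What the plan says.** Section 9.5 sizes minor defects through one row of Table 3, labelled "Specific pattern of 3 or more minor structural birth defects", with 60 infants in cohort 1, 120 in a comparison cohort, a 1% baseline, RR 10.0 and 71% power. The text says "A baseline prevalence estimate of 1% has been used for a specific pattern of minor" structural defects and "The RR detectable with this sample size is 10.0", which it equates with a 10% prevalence, or about 6 exposed children. Footnote e gives the basis of the 1%: "Baseline rate in comparison group expected to be 0-1% based on no evidence of a pattern". Footnote f gives the test: "Based on one-tailed Fisher's Exact Test, alpha 0.05". The same section introduces Table 3 as showing effects detectable at 80% power or more with "two-tailed tests of significance (except as noted below for pattern of minor structural" birth defects).

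Section 9.7.2.5.2 evaluates minor defects in two steps, among infants who had the dysmorphology examination. Step 1 is "A comparison among groups of the proportion of infants with any 3 or more minor" structural defects, made without looking at which defects they are. In step 2 the exposed "group will be examined for evidence of a specific pattern of 3 or more defects in any 2 or more children". Only if a pattern is found are Comparison Groups I and II checked for the same one.

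**The concern.** A power figure should belong to an analysis the plan sets out, and should follow from the inputs printed beside it. This row is doubtful on both counts.

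Step 1 uses a different outcome, any 3 or more defects, from an examination form with about 130 items (section 9.4.6). The 1% is the assumed frequency of one particular pattern and cannot stand in for that. Step 2 picks the pattern from the exposed infants' own data. A Fisher power calculation assumes an outcome fixed before the data are seen, so the row does not describe step 2 as written either.

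The stakes are in interpretation. Section 9.9 names pattern detection as the primary strength of the cohort, and section 9.5 rests the evaluation of teratogenic risk on the primary outcome together with evidence of a pattern. A negative minor-defect result would be read against RR 10.0 at 71%, the only figure given. That figure is miscalculated for its label and says nothing about the comparison in step 1.

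**Working it through.** **1. The printed figure.** Inputs, all from section 9.5 and Table 3: X ~ Bin(60, 0.10) in the exposed, Y ~ Bin(120, 0.01) in the comparison group, Fisher's exact test, one-tailed, alpha 0.05. Power = Σ P(Y = y) × P(X ≥ c(y)), where c(y) is the smallest exposed count with one-tailed p ≤ 0.05.

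| y | P(Y = y) | c(y) | P(X ≥ c) | product |
|---|---|---|---|---|
| 0 | 0.2994 | 3 | 0.9470 | 0.2835 |
| 1 | 0.3629 | 4 | 0.8626 | 0.3130 |
| 2 | 0.2181 | 5 | 0.7290 | 0.1590 |
| 3 | 0.0867 | 6 | 0.5628 | 0.0488 |
| 4 | 0.0256 | 7 | 0.3935 | 0.0101 |
| 5 or more | | | | about 0.0017 |

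The sum is 0.816, so one-tailed power is 81.6%. Two-tailed, only the y = 3 row changes materially: the cut-off becomes 7 and the product 0.0867 × 0.3935 = 0.0341. The sum is then 0.801, or 80.1%.

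Normal approximations at 60 against 120 do not give 71% either. Pooled they give 83.7% one-sided and 76.9% two-sided; with continuity correction 74.8% and 66.3%; unpooled 73.2% and 61.9%. A one-sided normal approximation with 60 against 60 gives 71.3% unpooled or 70.1% pooled, but the row states 120, and one-tailed Fisher at 60 against 60 gives 55.5%. The source of 71% cannot be settled from the protocol.

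**2. Step 1 as written.** The protocol gives no baseline for any 3 or more minor defects, so the baselines below are assumed. Two-tailed Fisher, alpha 0.05, 60 against 120, exact enumeration:

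| assumed baseline | RR | exposed rate | power |
|---|---|---|---|
| 2% | 6.5 | 13.0% | 80.6% |
| 5% | 3.9 | 19.5% | 81.3% |
| 10% | 2.8 | 28.0% | 82.5% |
| 15% | 2.3 | 34.5% | 81.0% |

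Sixty is an upper limit for the number examined. It counts every expected live birth, whereas section 9.7.2.4.1 restricts this analysis to examined infants.

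**3. Step 2 as written.** The trigger is that at least 2 exposed infants share a pattern. For one given pattern among 60 examined infants, P(trigger) = 1 − (1 − p)^60 − 60p(1 − p)^59.

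- p = 0.10: 1 − 0.0018 − 0.0120 = 98.6%.
- p = 0.01, the protocol's own background rate: 1 − 0.5472 − 0.3316 = 12.1%.

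Neither is the power of a test. They show that 71% does not describe how this rule behaves, and that a high detection probability comes with an appreciable false-trigger rate. Over all the patterns possible on the form, the chance that some pattern triggers by accident could be higher than 12.1%.

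**The case against.** A reader might infer that the pattern test is never run. The protocol does not support that. Section 9.3.2.2.2 makes pattern part of a secondary outcome, section 9.7.2.5.2 compares all secondary outcomes with each comparison group, and section 9.7.2.1 provides for significance testing in the cohort analysis. Section 9.5 also anticipates a test for pattern that is not two-tailed. Step 2 would yield the counts a Fisher test needs, and naming the test may be left to the statistical analysis plan, which is not at hand. What stands is narrower: section 9.7.2.5.2 specifies no test for this step, and a pattern selected from the exposed data is not the fixed outcome the printed calculation assumes.

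A reader might also take the one-tailed choice as an error. It is disclosed in the text and in footnotes b and f, and is not a contradiction.

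Nor need a protocol power every secondary outcome. Table 3 has no rows for elective abortion, serious infections, vaccine reactions or breastfeeding. The protocol also ties the 1% to a specific pattern and never applies it to any 3 or more defects. So the missing line for step 1 is not an error by itself. It matters because the one minor-defect figure that is printed describes something else.

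Finally, the exception worded in section 9.5 could be stretched to cover the 80% threshold. It follows the words on two-tailed testing, so the plainer reading is that it concerns sidedness alone. Either way, 71% remains wrong for its stated test.

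**Conclusion.** The point holds in two parts. First, 71% is not the power at the stated inputs; the exact value is 81.6% one-tailed or 80.1% two-tailed. This rests only on the protocol's own numbers. The error understates power, and correcting it would also remove the conflict with the 80% statement in section 9.5. Second, the row matches neither step of section 9.7.2.5.2: step 1 has another outcome and no baseline, and step 2 has no specified test and a data-selected pattern.

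The RR values of 6.5 to 2.3 for step 1 depend on assumed baselines and on all 60 and 120 infants being examined. They illustrate what an applicable row would look like and are not evidence of an error. The defect lies in a stated power figure and its fit with the analysis text. It does not undermine the design or the primary comparison, but it should be put right before minor-defect results are interpreted.

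**What to change.** 1. In Table 3, replace 71% by 81.6% (one-tailed Fisher at the stated inputs), or remove it.
2. In section 9.7.2.5.2, state whether the pattern step is descriptive or tested. If descriptive, drop the power and the detectable RR of 10.0 for it in section 9.5. If tested, name the test and its sidedness, and say how it allows for a pattern found in the exposed data.
3. Make the minor-defect row describe step 1: any 3 or more minor defects, two-tailed, with the number expected to be examined and a sourced baseline. Section 9.4.6 reports well over 1400 infants examined under the same procedures. That is a natural place to look, although the protocol does not say a suitable baseline can be drawn from it.
4. If a detection probability is given for the rule of 2 or more children (98.6% for a 10% pattern in 60 examined infants), print the false-trigger probability beside it: 12.1% for one pattern at 1%, and possibly more over all patterns.

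The cost is an edit to one table row and two paragraphs, plus finding a baseline. Design, sample size and data collection do not change.
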